4.1 General Study Design

This is a randomized 1:1 non-inferiority trial of the new diagnostic algorithm versus the current standard of care. A non-inferiority design has been chosen to reflect the clinically most important outcome (diagnostic accuracy) in the presence of a technology which is likely to reduce significant current complications / adverse events, and allow in the same procedure mediastinal staging and, potentially, additional bronchoscopic interventions (such as airway inspection, biopsy of additional nodules).

4.2 Patient Inclusion and Exclusion Criteria

Inclusion criteria:

1. Patient is \geq 18 years of age at time of signing informed consent .
2. Patient is referred for biopsy of a single indeterminate pulmonary nodule, with the following characteristics regarding size, location, accessibility, and probability of malignancy:
 - a) Intermediate or high pre-test probability of malignancy as defined by a pre-test probability of malignancy between 10% and 100%, using a validated clinical prediction model, which is either:
 - i. The Brock model¹⁴ if no PET scan data are available, or
 - ii. The Herder model¹⁵ if PET-CT data are available.
 - b) Size between 10 and 30 mm (long diameter).
 - c) Location peripheral, here defined as occupying the middle or outer third lung zones.
 - d) Accessible via navigation bronchoscopy and also accessible via CT-guided biopsy (i.e. the nodule is clinically suited to equal access by either procedure), as confirmed by an independent interventional panel (see Section 4.5).

Note: Prior to randomization, the main purpose of this study-provided central review is to establish panel agreement with local expertise offered by the participating study site, that local management of a consented candidate patient at the site can be achieved by standard of care navigation

CONFIDENTIAL

bronchoscopy or equally achieved by standard of care CT-guided biopsy (with either procedure able to be performed at the local institution).

Exclusion criteria:

1. Patients with proximal nodules, as defined by nodules present in the proximal 1/3 of the lung by dedicated software analysis (described below) will not be eligible for the study.
2. Patients with multiple nodules requiring biopsy (patients may have other nodules not considered for biopsy).
3. Radiologically abnormal mediastinal or hilar lymph nodes requiring endobronchial ultrasound.
4. Patients for whom stereotactic body radiation therapy is planned even if biopsies show no evidence of malignancy.
5. Patients with contraindication to biopsy or deep sedation/general anesthesia.
6. Patients unable or unwilling to comply with study follow-up schedule.
7. Patients previously randomized to the study.
8. Patients unable to provide documented informed consent.
9. Patients who are nursing or pregnant as verified by an optional standard of care pregnancy test. (Testing required only if deemed clinically necessary by the patient's study physician.)

4.3 Withdrawal of Patients

The reasons for study exit of all enrolled patients will be documented on the applicable case report form electronic case report form (eCRF). In the event patient withdraws consent during the study, the date of withdrawal will be documented. If the study investigator voluntarily removes a subject from further study participation, supporting documentation must be in place for the rationale and date of removal. Every attempt will be made to contact patients who are non-compliant: subjects will be considered lost to follow-up once the following steps have been taken:

- Two phone calls should be made to the patient. Each attempt should be clearly documented in the source documents and the response or lack thereof should be captured.
- If there is no response to the phone calls, then certified letter should be sent. A copy of the letter will be kept on record.
- After a period of two weeks after the aforementioned interventions, the patient will be considered lost to follow-up. Study exit form will be completed.

CONFIDENTIAL

4.4 Patient Flow

Potential candidate patients in the standard of care setting will be evaluated by a lung nodule expert at the study site for the presence of a single 10-30mm (longest diameter) indeterminate peripheral lung nodule with a pre-test probability of malignancy between 10% and 100%. Consented patients will subsequently receive additional review by central expert opinion provided by the study, in order to verify the patient's single indeterminate peripheral lung nodule is suitable for both navigation bronchoscopy and CT-guided biopsy.

4.5 Image Transfer and Interventional Panel Adjudication

An independent expert interventional panel composed of an interventional pulmonologist and an interventional radiologist will review the chest CT of screened patients to confirm suitability for navigation bronchoscopy and CT-guided biopsy. Neither expert will be aware of the other's decision. The panel is required to give a view if either of these techniques is technically feasible (and not which is "better"), with the interventional pulmonologist assessing the feasibility of navigation bronchoscopy and the interventional radiologist assessing that of CT-guided biopsy. Each participating institution receives an institution-wide account of the LungCloud™ platform. The LungCloud™ is provided by Neurotargeting LLC, a spin-off of Vanderbilt University. The LungCloud™ is a health IT clinically approved system for the collection of complete data sets in the clinical flow, including but not limited to clinical outcome, radiology notes and scans. The LungCloud™ is set up as a network of accounts that can be interconnected around a clinical study. The managing institution creates a Clinical Trial inside the LungCloud™ and ties it to each of the institutions. Each institution is then able to collect and share data for the clinical study. Data is collected in the clinical flow and from PACS and stays at all time in the LungCloud™ instance of the institution owning the data.

Image data is encrypted and sent to the institution's LungCloud™. Automatic uploading of images is achieved through what is referred to as the LungDrive. This is a process that runs on the end user's machine and works in a way similar to Box or Dropbox, i.e., any new image volume placed in a specific folder is automatically encrypted and uploaded to the account repository. The non-imaging data can be entered into the system and associated with the imaging data through web-based forms customized to the end users. Images are reconstructed in 3D and can be reviewed in any view (sagittal, coronal or axial). The system offers a series of web-based user interfaces that permit inspecting and visualizing both imaging and non-imaging data.

The LungCloud™ allows each site's clinical study coordinator to manage patients that have to be added to the clinical study. Informed consent can be electronically acquired or added manually in the system. After informed consent has been obtained, the patient's de-identified data will be shared with the study primary site.

As part of the study, the subject's chest CT will be displayed in the clinical study review web-portal for analysis by the independent interventional panel consisting of (1) an interventional pulmonologist expert in navigation bronchoscopy and (2) an interventional radiologist expert in CT-guided biopsy. The lung nodule will be assessed for its location in the proximal, middle or outer third of the lung by an independent expert lung nodule physician using a validated software analysis. Nodules accessible by ultrasound guided TTNA, conventional bronchoscopy or linear EBUS will be excluded. Nodules located in the middle or distal third will be included. If

CONFIDENTIAL

the nodule is deemed amenable to both bronchoscopic and CT-guided biopsy approach, the patient will be randomized.

This assessment involving central review by the interventional panel is intended to occur within **3 business days** after informed consent is obtained. Subsequent randomization of eligible patients is anticipated in conjunction with confirmation of enrollment (as outlined below in Section 5), with initiation of navigation bronchoscopy or CT-guided biopsy to occur within 3 weeks (30 calendar days) after a site is notified of randomization. In the event that a CT scan cannot be uploaded to LungCloud™ expeditiously enough for adjudication to occur within the mandatory 3 day post-informed consent window, central adjudication will proceed using one or multiple representative axial CT slices uploaded to CRF 2 in the study REDCap database.

[figure not shown]
Exclusion criteria for accessibility via navigation bronchoscopy:

1. Nodules with an airway greater/equal to 3 cm away from the lung nodule
2. Nodules located in areas deemed unreachable by an expert interventional bronchoscopist

Exclusion criteria for accessibility via CT-guided biopsy:

1. All nodules for which a fissure would have to be crossed
2. All nodules for which a large bulla would have to be crossed
3. All nodules located in areas deemed unreachable by expert interventional radiologist

To determine if a nodule falls into the outer 1/3, middle 1/3 or proximal 1/3 of the lung parenchyma, proprietary software will be utilized to map zones of the lung as previously described.¹⁶ “CT Pulmo 3D” workflow using OsiriX which automatically analyzes the lung parenchyma and defines the contours of both lungs. If a nodule is within the outer 2/3 of the lung parenchyma or the nodule touches the border of the outer 2/3 of the lung parenchyma the nodule will be considered candidate for study. Each site will be provided with the zone of the nodule (outer, middle or inner 1/3) and an image of the lung zones and nodule prior to the procedure. The figure below depicts an example of lung segmentation and outer 1/3 determination using CT Pulmo 3D.

CONFIDENTIAL

4.6 Intervention Arm: Bronchoscopy Pathway

The intervention arm will consist of electromagnetic (EMN) navigation bronchoscopy using the Medtronic SuperDimension platform with F-Nav. Patients' available DICOM CT images will be uploaded into the planning software. CTs obtained more than 21 days before the planned procedure, and CT not meeting minimal technical requirements for optimal roadmap planning (adequate CT reconstructions and slice thickness of 1.5mm or less) will be repeated before the procedure. Bronchoscopy will be performed by interventional pulmonologists with expertise in navigation bronchoscopy (as defined by more than 100 procedures performed in the past 2 years, with at least 25 of these performed with F-Nav). Procedures will be performed under general anesthesia with neuromuscular blockade (to facilitate breath holds required for FNAV image acquisition) in a dedicated bronchoscopy suite or operating room. Bronchoscopy will be performed as previously described with confirmation by radial ultrasound.¹⁷ Suggested intraprocedural flow is detailed in the figure in section #14. Radial ultrasound will be used for confirmation only, and not as a navigational tool (i.e. catheters not aligned with the registered target will be considered non-diagnostic). Biopsies will be obtained using a any-gauge needle, with at least 5 passes obtained per nodule. Forceps biopsies, brushings or other biopsy tools will be performed according to the procedure algorithm. Rapid on-site evaluation will be performed to assess for specimen adequacy. All procedures will be followed by fluoroscopy evaluation of the chest to exclude pneumothorax, and, if indicated, ultrasound and/or formal chest radiograph as per standard of care. The procedure will be deemed non-diagnostic if the proceduralist is unable to reach the nodule or if a complication occurs and therefore no biopsy is obtained.

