The diagnostic algorithm for indeterminate pulmonary nodules is based on pre-test probability of malignancy as determined by validated clinical prediction scores or clinician estimates. Low-probability (<10% chance of malignancy) are followed radiologically with serial CT, while high pre-test probability nodules (>70% chance of malignancy) are typically surgically resected, although tissue confirmation is often necessary even for these nodules.⁵ A non-surgical biopsy is typically recommended for nodules with low to intermediate probability of malignancy. High pre-test probability nodules are also frequently biopsied, when surgery is considered higher-risk or when stereotactic body radiation therapy is considered. Options include CT-guided transthoracic needle biopsy or bronchoscopic biopsy. CT-guided biopsy is associated with a general yield estimated at 90%, although studies focusing on nodules < 1.5 cm have reported yields between 70% and 80%.⁶⁻⁸ There has not been randomized controlled studies comparing CT-guided biopsy to other approaches. The technique is associated with substantial complications: in a population-based study, the rate of pneumothorax was 15% with need for chest tube management in 7%, and the risk of hemorrhage was 1%.⁹ Conversely, bronchoscopic biopsy is safer with reported 1.6% pneumothorax, with a need for chest tube management in 0.7%, and a 0.5% hemorrhage risks, but best estimates of yield using conventional navigation techniques approach 75%, with rates below 50% in registry data.¹⁰⁻¹²

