3.2 Aims and Objectives

In this study, we propose to study in a 1:1 randomized controlled trial the diagnostic accuracy of navigation bronchoscopy (NB) with F-Nav (SuperDimension iLogic 7.2 ENB platform and later (SuperDimension, Medtronic, Minneapolis, Minnesota, USA)) using a non-inferiority study design (primary endpoint) versus the current clinical standard of care: CT-guided biopsy. We will in addition compare: complications rate including rate of pneumothorax and clinically significant bleeding, need for hospitalization

CONFIDENTIAL

after procedure, time to procedure, duration of the procedure, need for additional nodule biopsy, need for additional procedure for staging, radiation exposure from fluoroscopy and CT, and need for F-Nav during navigation bronchoscopy (secondary endpoints). Follow up has been chosen to be pragmatically deliverable while allowing full assessment of key outcomes, including false negatives to provide a robust, clinically meaningful trial result.

4. Study Design

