4.7 Comparison: CT-guided Biopsy Pathway

The control arm of the study will consist of CT-guided biopsy, which will be performed by interventional radiologists with expertise in transthoracic needle biopsy and/or fine needle aspiration (as defined by more than 25 procedures performed in the past two years as a department). Procedures will be performed in a dedicated interventional CT scanner with multi-slice capabilities. Patient analgesia with local anesthesia and moderate conscious sedation will be used. Biopsy number, core biopsy vs. fine needle aspiration, use of coaxial needles, and use of rapid on-site cytologic examination will be at the discretion of the proceduralist per local institutional preferences. Procedures will be followed by limited CT scan and/or chest radiograph to exclude pneumothorax if required per local standard of care. The procedure will be deemed non-diagnostic if the proceduralist is unable to reach the nodule or if a complication occurs and therefore no biopsy is obtained.

- 1. Patients not eligible for general deep sedation and general anesthesia and therefore not eligible for bronchoscopy, but potentially eligible for CT-guided biopsy, will be excluded from the study but recorded as such in the CONSORT diagram.**
- 2. Patients randomized who fail to present for their assigned intervention will be considered screen-failure**
- 3. Patients randomized who present for their assigned intervention but do not undergo the procedure for reasons other than for contraindications to the procedure (per institutional policy) will be analyzed as non-diagnostic procedure, and otherwise considered screen-failure. The cause for cancellation will be recorded in the case report form.**

CONFIDENTIAL

See Procedural Flow Chart (Section 14).

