4.8 Outcomes

Primary endpoint

The primary endpoint will be diagnostic accuracy, as defined by the rate of technically successful biopsies leading to a definitive diagnosis, comparing the navigation bronchoscopy to the CT-guided biopsy pathway. Definitive diagnoses are pre-defined as any of the following:

- Malignancy on histological samples, **OR**
- Biopsies with abnormal tissue (excluding normal or absence of lung parenchyma) that are followed by a surgical lung biopsy yielding the same histological diagnosis, **OR**
- Specific benign histopathologic finding which accounts for the presence of a lung nodule (specifically including organizing pneumonia, frank purulence, granulomatous inflammation, or other specific benign finding) **AND**
- Absence of malignancy (true negative) over 1 year of longitudinal CT follow-up, defined as:
 - the nodule markedly regresses or resolves on follow-up imaging, **OR**
 - a persistent nodule has not been diagnosed as malignant, **AND**
 - there are no plans for repeat invasive diagnostic procedures through 12 months follow-up.

Biopsies with normal or absence of lung parenchyma, atypia or mild inflammation will be considered non-diagnostic. All diagnoses (from both arms) will be determined by a blinded, independent, expert lung pathologist (i.e. blind to the biopsy technique) and all non-diagnostic biopsy specimens will be reviewed by an independent expert pathologist.

Linear EBUS for lymph node interrogation and staging will be performed in the same procedure after the navigation bronchoscopy for staging purposes as per standard of care.

Secondary endpoints

- Rate of pneumothorax
- Rate of pneumothorax requiring chest tube placement
- Clinically significant bleeding (defined by bleeding requiring intervention)
- Need for hospitalization after procedure
- Duration of the procedure (from bronchoscope in to bronchoscope out for the bronchoscopy arm and from first needle in to last needle out for CT-guided biopsy)
- Procedural factors associated with improved yield (type of biopsy, number of biopsies, use of radial ultrasound, presence of a bronchus sign, biopsy site)
- Need for additional nodule biopsy
- Need for additional procedure for staging

CONFIDENTIAL

- Radiation exposure from fluoroscopy-guided bronchoscopy and CT for CT-guided biopsy
- Need for F-Nav during navigation bronchoscopy
- Adequacy of specimens collected for molecular testing when needed.

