7.1 Grading

Adverse events will be graded according to the NCI's Common Terminology Criteria for Adverse Events (NCI CTCAE), Version 5.0, dated November 27, 2017, currently locatable via the following URL:
https://ctep.cancer.gov/protocoldevelopment/electronic_applications/docs/CTCAE_v5_Quick_Reference_8.5x_11.pdf

CONFIDENTIAL

If events are not listed in the CTCAE, severity may be designated as mild, moderate, severe, life-threatening, or fatal which respectively correspond to Grades 1, 2, 3, 4, and 5 on the NCI CTCAE, with the following definitions:

- **Mild:** Asymptomatic or mild symptoms; clinical or diagnostic observations only; intervention not indicated;
- **Moderate:** Minimal, local or noninvasive intervention indicated; limiting age-appropriate instrumental activities of daily living (ADL) such as preparing meals, shopping for groceries or clothes, using the telephone, managing money, etc;
- **Severe:** Medically significant but not immediately life-threatening; hospitalization or prolongation of hospitalization indicated; disabling; limiting self care ADL such as bathing, dressing and undressing, feeding self, using the toilet, taking medications;
- **Life-threatening:** Urgent intervention indicated to prevent risk of death present at the time of the event;
- **Fatal:** An event that results in the death of the patient.

Information on adverse events, whether serious or not, whether reported by the participant, directly observed, or detected by physical examination, laboratory test or other means, will be collected, recorded, followed and reported as described in the following sections.

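### The rate of any pneumothorax is compared between arms that look for pneumothorax differently, so the difference mixes procedure risk with detection, in a direction the documents do not settle

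*Combined protocol and SAP*

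**What the plan says.** For the bronchoscopy arm, Section 4.6 states: "All procedures will be followed by fluoroscopy evaluation of the chest to exclude pneumothorax". Ultrasound or a formal radiograph is added only if indicated.

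For the CT-guided arm, Section 4.7 states: "Procedures will be followed by limited CT scan and/or chest radiograph to exclude pneumothorax if required per local standard of care". These biopsies are done in an interventional CT scanner.

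Section 4.8 lists two pneumothorax endpoints among the secondary outcomes: "Rate of pneumothorax" and "Rate of pneumothorax requiring chest tube placement". The first has no criterion for size, symptoms, treatment, detecting modality or time. The bleeding endpoint in the same list does have a threshold, because it counts only bleeding that needs intervention.

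Section 3.2 makes the comparison between arms explicit: "We will in addition compare: complications rate including rate of pneumothorax and clinically significant bleeding, need for hospitalization".

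**The concern.** An unthresholded count of pneumothorax depends on how hard one looks and with what. Here the arms differ in modality, in whether imaging is universal and, within the CT-guided arm, possibly by site. The count is then not the same measurement in the two arms.

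This matters because fewer complications are part of the case for bronchoscopy (Sections 3.1 and 4.1), and Section 6.1 refers to the pneumothorax rate of CT biopsy when it justifies the 10-point margin. Readers will set the observed pneumothorax difference against any loss of accuracy. They need that difference to describe the procedures and not the imaging that followed them.

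**Working it through.** **Does anything in the text equalise detection?** The places that could do so, in turn:
- Blinded central review (Sections 4.8 and 4.9) covers pathology only.
- The contact at 7 to 10 days (Section 16) is common to both arms, but is by telephone, clinic visit or chart review.
- Chest CT in the Section 16 table is marked as standard of care, and Section 4.9 suggests scans at 3, 6 and 12 months.
- Section 6.3 lists pneumothorax as a recorded complication without an ascertainment standard. Section 7.2 tells sites not to record non-serious events related to either procedure.
- The flow chart in Section 14 is not shown, so it cannot be checked.

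No readable text equalises detection. The condition in Section 4.7 could be read as attaching only to the radiograph. Even then, fluoroscopy is compared with CT and/or radiograph.

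**Sample size.** The plan gives no power figure for pneumothorax. Its primary-endpoint figure reproduces: (1.645 + 0.842)² × 2 × 0.9 × 0.1 / 0.10² = 111.3, so 112 per group, and 112 × 1.15 = 128.8, so 129 per group. I use 129 per arm.

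**Method.** Observed rate = true rate × fraction detected. The chance of a significant result is the sum of the binomial probabilities of all pairs of counts for which Fisher's exact test gives two-sided p < 0.05. The detection fractions are assumptions, and so is the test, because the plan names none for secondary endpoints.

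**Case 1: equal true rates (assumed).** NB is the bronchoscopy arm and CT the CT-guided arm.

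| True rate | Detected NB / CT | Observed NB v CT | Difference (points) | Chance of false significance |
|---|---|---|---|---|
| 10% | 100% / 100% | 10% v 10% | 0 | 1.5% in each direction |
| 10% | 50% / 100% | 5% v 10% | 5 | 25%, favouring NB |
| 10% | 100% / 50% | 10% v 5% | 5 | 25%, favouring CT |
| 10% | 70% / 90% | 7% v 9% | 2 | 5%, favouring NB |
| 10% | 30% / 100% | 3% v 10% | 7 | 54%, favouring NB |
| 15% | 70% / 90% | 10.5% v 13.5% | 3 | 8%, favouring NB |
| 15% | 30% / 100% | 4.5% v 15% | 10.5 | 78%, favouring NB |

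With equal arms, swapping the two detection fractions reverses the favoured arm and leaves the probability unchanged. Every row therefore has a mirror image. With 112 per arm, the rows 5% v 10%, 7% v 9% and 3% v 10% give 22%, 5% and 48%.

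**Case 2: the rates cited in Section 3.1 are the true rates** (15% CT-guided, 1.6% bronchoscopy). With full detection the difference is 15 − 1.6 = 13.4 points, the ratio is 9.4, and the test favours bronchoscopy in about 98% of trials. Now let detection run over 40-100% for bronchoscopy and 50-100% for CT-guided biopsy (assumed):
- Smallest gap: 15 × 0.5 − 1.6 × 1 = 7.5 − 1.6 = 5.9 points, ratio 4.7. The same enumeration favours bronchoscopy in about 52% of trials.
- Largest gap: 15 × 1 − 1.6 × 0.4 = 15 − 0.64 = 14.4 points, ratio 23.4. It favours bronchoscopy in more than 99% of trials.

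The sign holds throughout, but the size does not.

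**The case against.** The strongest reply is that the protocol expects 15% v 1.6%, a gap that detection differences of the assumed size do not reverse. The list also already includes chest-tube placement and hospitalization, both less dependent on screening imaging, and both arms have the same follow-up contact. All of this stands. It limits the point to the size of one secondary comparison, but it does not make that comparison like-for-like.

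Two stronger readings are tempting, and the documents do not support them.
- A reader might infer that the imaging is biased towards bronchoscopy and would manufacture a safety benefit. That needs CT-arm imaging to be near universal and fluoroscopy to miss more. Section 4.7 leaves imaging to local practice, and the documents give no detection figures. The reverse bias is equally open.
- A reader might infer that the non-inferiority conclusion is affected. Section 6.1 rests the margin on the known pneumothorax rate of CT biopsy and on a poll of clinicians. The rate observed in this trial enters neither the margin nor the decision rule in Section 6.2.

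**Conclusion.** The point holds as a measurement problem in one secondary endpoint. As planned, the difference in any pneumothorax combines procedure risk with detection, in an unsettled direction. Its size depends on assumed detection fractions. With an equal true rate of 10%, halving detection in one arm gives a false result in about 25% of trials, in either direction. With the cited rates as truth, the difference keeps its sign but is observed anywhere from 5.9 to 14.4 points against a true 13.4. The primary endpoint and its sample size are untouched. This is a worthwhile, inexpensive improvement; it does not threaten the trial's main conclusion.

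**What to change.** 1. In Section 4.8, base the between-arm comparison on clinically significant pneumothorax, defined identically in both arms as pneumothorax requiring intervention or hospital admission within the 7-day window of Section 7.2. This parallels the bleeding definition and sits beside the chest-tube endpoint.
2. Report any pneumothorax descriptively by arm, by whether post-procedure imaging was done and by detecting modality. State that it is not like-for-like, and that the threshold in item 1 reduces dependence on imaging without removing it, since an imaging finding can itself prompt treatment or admission.
3. Add two case report form items: imaging done, and detecting modality.
4. Reconcile Section 7.2 (non-serious procedure-related events not recorded) with Section 6.3 (pneumothorax recorded as a complication), so that minor events are captured alike in both arms.

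A threshold at grade 2 of Section 7.1 would be less clean. Its definitions apply only to events not listed in CTCAE, and its lowest grade reads "Asymptomatic or mild symptoms; clinical or diagnostic observations only; intervention not indicated", so a symptomatic event is not necessarily above grade 1.

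The cost is one definition, two form items and one clarification. Clinical imaging does not change. The downside is fewer counted events and less precision. The new endpoint counts at least the chest-tube cases. At the cited 7% v 0.7% for those alone, the chance of significance with 129 per arm is about 69% by the Fisher enumeration (75% by normal approximation), against about 98% for any pneumothorax at 15% v 1.6%.
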